#### ANALYSIS PLAN

Data will be entered into a secure Microsoft Access database. Entry to the database is limited to key personnel and is password protected at the point of the workstation and the application. Standard double-entry and data checking approaches will be performed for all measures.

General Analytic Approach: Descriptive statistics will be performed on all study variables. In order to mitigate potential bias due to transient improvements in either sleep or BP dipping, we will utilize a 6-wk run-in phase after which participants will have their sleep efficiency and BP dipping markers re-assessed to ensure stability. Although we do not anticipate significant variation in either sleep or BP parameters during this pre-treatment phase, we will exclude participants who no longer meet inclusion criteria following the 6-wk run-in period. This practice has been shown to result in an increased magnitude of treatment improvements and therefore may improve the statistical power and potential precision of the proposed analyses. Markers of sleep efficiency and BP dipping collected after our run-in phase will therefore be used as our baseline assessment measures.

Regression-based analytic approaches will be used to examine associations between improved sleep efficiency, ABP indices, and mechanisms of CVD risk. In order to minimize potential confounding of treatment improvements due to either misdiagnosis or transient fluctuations in sleep, we will use assessments collected after the run-in period as our baseline time point. For our 6-week outcomes, improvements in sleep efficiency and ABP will be examined using simple regression analyses as detailed below. In contrast, our 6-month outcomes will be examined using repeated measures mixed models with an unstructured covariance matrix, using both 6-week and 6-month levels of the outcome modeled jointly. Incorporating both outcomes into a unified, mixed modeling approach will allow us to examine improvements in sleep as they associate with trajectories of BP dipping improvements and also allows for more robust handling of missing data.

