For our primary aim examining improvements in sleep efficiency and ABP, we will focus on nighttime BP dipping as the outcome of interest with a prespecified significance level of  $P = .05$ . Because other ABP outcomes could plausibly be improved with CBT-I and will partially reflect improvements in nighttime dipping, we will conduct parallel analyses of nighttime average BP and 24-hour BP levels. Consistent with contemporary recommendations examining secondary outcome measures as supportive and/or explanatory, we will maintain a  $P = .05$  for all for secondary outcome measures. Patterns of missing data will be characterized using Rubin's criteria and managed accordingly using Harrell's multiple imputation (mult.impute) procedure in R. We will carefully examine all model assumptions and reparameterize as indicated. All analyses will be carried out using SAS (Cary, NC) or R (<http://cran.r-project.org/>) software.

**AIM 1:** Determine whether the circadian BP profile contributes CVD risk associated with poor sleep by evaluating whether it is modified by changes in sleep quality in men and women with hypertension and comorbid insomnia

**Hypothesis 1:** Improved sleep quality will be accompanied by: (i) enhanced nighttime BP dipping; (ii) lower average nighttime BP; (iii) lower average 24-hour BP.

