**Analysis Plan:** General linear models will be used to examine the associations between improvements in sleep quality on improvements in BP dipping, controlling for age, gender, race, baseline sleep efficiency, baseline mean 24-hour BP, and pretreatment BP dipping, with post-treatment BP dipping as the criterion. Significance will a priori be set at  $P = .05$ . For follow-up analyses of 6-mo BP dipping, linear repeated measures mixed models will be examined in which 6-wk and 6-mo BP dipping both serve as outcome variables using the same covariates above. As an a priori explanatory analysis for our follow-up analyses, we will examine potential time X sleep efficiency interactions in order to examine the extent to which the association between sleep efficiency and BP dipping at six weeks differs from that at six-months. In addition, we will conduct an area under the curve analysis to examine overall associations that apply to both 6-wk and 6-mo in order to determine whether larger improvements in sleep are associated with larger improvements in BP outcomes in an overall sense. Because other ABP outcomes could plausibly be improved by CBT-I and also will reflect improved nighttime dipping, we will conduct parallel analyses of nighttime average BP and 24-hour BP levels.

**AIM 2:** Evaluate candidate mechanisms of CVD risk related to sleep quality in patients with hypertension and comorbid insomnia

**Hypothesis 2:** Improved sleep quality will be accompanied by: (i) reduced nighttime SNS activity; (ii) enhanced vascular endothelial function; (iii) reduced arterial stiffness, and; (iv) improved lipid profile.

**Analysis Plan:** General linear models will be used to examine the associations between improved sleep efficiency and improvements in mechanisms of CVD risk, controlling for age, gender, race, baseline sleep efficiency, and the pre-treatment (post run-in) level of the outcome. For our analyses of vascular endothelial function only, we also will adjust for baseline arterial diameter, consistent with our prior work. Follow-up analyses will follow the same approach as in Hypothesis 1, using linear repeated measures mixed models with 6-wk and 6-mo levels serving as the outcome variables.

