Power and Sample Size Considerations: Our power estimates were derived from prior data assessing sleep efficiency and nighttime BP dipping among individuals with HTN using the following assumptions: an initial sample size of 150 individuals, attrition of 15%, an alpha of 0.05, and a correlation of  $r = 0.30$  between sleep efficiency and BP dipping. Using these assumptions, we will have 80% power to detect correlations of  $r \geq 0.25$  between improvements in sleep efficiency and BP outcomes, suggesting that we will have adequate power to test the proposed hypotheses. In a more conservative scenario for comparing the worst 1/3 of the sample in terms of sleep efficiency change to the best 1/3, and assuming 50 participants in each group, there is 0.85 power at the two-sided 0.05 significance level for the detectable effect size  $\theta = 0.6$  via the following equation:  $(n \text{ per group}) = 50 = 2 * (((1.96 + 1.04) / 0.6) ** 2)$ . In the present proposal, this corresponds to a difference of 2.2% in SBP dipping between high and low sleep efficiency groups.

Exploratory Analyses of Effect Modification: In addition to our formal analyses, we will conduct exploratory analyses of effect modification, which will be interpreted as hypothesis generating. Candidate markers for effect modification will include background and clinical characteristics, such as race, gender, baseline insomnia severity, baseline anxiety, and the presence of elevated depressive symptoms ( $BDI > 14$ ). Specifically, we will examine the interaction terms between these candidate moderators, changes in sleep efficiency and mechanisms of CVD risk using the same general linear modeling approach noted for Hypothesis 2.

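### The joint 6-week/6-month model specifies no covariate-by-time terms, so a fading effect of pre-treatment dipping could bias its explanatory time × sleep efficiency term

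*Combined protocol and SAP*

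**What the plan says.** The Analysis Plan uses two kinds of model. For the 6-week results, "For our 6-week outcomes, improvements in sleep efficiency and ABP will be examined using simple regression analyses as detailed below"; under Aim 1 that is a general linear model for post-treatment dipping, "controlling for age, gender, race, baseline sleep efficiency, baseline mean 24-hour BP, and pretreatment BP dipping". For the 6-month results, the General Analytic Approach specifies "repeated measures mixed models with an unstructured covariance matrix", with the two visits modelled together. Aim 1 describes this model as one in which "6-wk and 6-mo BP dipping both serve as outcome variables using the same covariates above".

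One time interaction is named: "we will examine potential time X sleep efficiency interactions". It is labelled an a priori explanatory analysis, and its purpose is to examine "the extent to which the association between sleep efficiency and BP dipping at six weeks differs from that at six-months". No covariate-by-time term appears anywhere. Aim 2 says that its follow-up analyses take the same approach.

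**The concern.** A measurement taken before treatment often predicts a value some weeks later better than a value several months later. This trial offers a reason for that. Under Safety Monitoring, participants receive their blood pressure records at about 12 weeks and may start antihypertensive drugs at any time, so the 6-month values may have moved further from baseline.

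If the slope of pre-treatment dipping falls between the visits and the model allows one slope, the unmodelled difference has to go somewhere. An unstructured covariance matrix frees the residual variances and their correlation, but not the regression slopes. The only covariate whose slope may differ by visit is sleep efficiency, so its interaction picks up whatever part of the fading is correlated with it.

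Change in sleep efficiency is not randomised, because everyone receives CBT-I, so a correlation with baseline dipping cannot be ruled out. What is at stake is the reading of the 6-month visit: the interaction could suggest fading or strengthening when the sleep slope is the same at both visits.

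**Working it through.** **The plan's own figure.** Power and Sample Size Considerations assumes "an initial sample size of 150 individuals", 15% attrition and alpha 0.05, and claims 80% power for r = 0.25. With 150 × 0.85 = 127.5, taken as 127, power = Φ(atanh(0.25) × √124 − 1.96) = 0.81. The figure reproduces and is not in question.

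**Formula.** Let B be pre-treatment dipping and S the change in sleep efficiency, both in standard-deviation units, with slopes b₁ and b₂ for B at 6 weeks and 6 months. With complete data, two visits, unstructured covariance and one common slope for B, the time × S estimate equals the least-squares slope of (6-month minus 6-week dipping) on S alone. If the true S slope is the same at both visits,

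bias = (b₂ − b₁) × r(S,B).

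**Inputs.**
- From the plan: n = 127, and r = 0.30 between sleep efficiency and dipping.
- Assumed: correlation −0.5 between S and baseline sleep efficiency (change contains baseline with a negative sign); partial correlation p of S with B, given baseline sleep efficiency, from −0.2 to 0.3; slopes 0.6 to 0.4 or 0.65 to 0.35; residual standard deviation 0.75; residual correlation 0.4; S is the fixed 6-week change.

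**Steps.**
1. r(S,B) = −0.5 × 0.30 + p × √(0.75 × 0.91) = −0.15 + 0.826p.
2. Residual variance of the difference = 2 × 0.75² × (1 − 0.4) = 0.675.
3. Standard error of the interaction as planned = √{[0.675 + (b₂ − b₁)²(1 − r(S,B)²)]/127}.
4. Rejection = P(|Z + bias/standard error| > 1.96).

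| p | r(S,B) | slopes | bias | standard error | rejection |
|---|---|---|---|---|---|
| −0.2 | −0.315 | 0.6 to 0.4 | +0.063 | 0.075 | 13% |
| −0.2 | −0.315 | 0.65 to 0.35 | +0.095 | 0.077 | 23% |
| 0 | −0.150 | 0.6 to 0.4 | +0.030 | 0.075 | 7% |
| 0 | −0.150 | 0.65 to 0.35 | +0.045 | 0.077 | 9% |
| 0.3 | +0.098 | 0.6 to 0.4 | −0.020 | 0.075 | 6% |
| 0.3 | +0.098 | 0.65 to 0.35 | −0.029 | 0.078 | 7% |

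Rejection is at its nominal 5% where r(S,B) = 0, that is at p = 0.15/0.826 = 0.18. If b₁ = b₂ there is no bias at any p.

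**Check with missing data.** Likelihood fits to 2,000 simulated trials per setting (150 participants, 15% missing at 6 months, B the only covariate, slopes 0.6 to 0.4) gave bias −0.060 and 11.7% rejection at r(S,B) = +0.3, +0.059 and 9.3% at −0.3, and about ∓0.02 and 6% at ±0.1. The formula gives ∓0.06 and ∓0.02. With time × B added, the mean estimate was within 0.004 of zero and rejection was 3.9% to 6.0% in every setting.

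**Precision.** With time × B, the standard error is √{0.675/[127 × (1 − r(S,B)²)]} = 0.073 to 0.077, against 0.075 to 0.078 without it. Adding time × baseline sleep efficiency as well gives √{0.675/[127 × 0.75 × (1 − p²)]} = 0.084 to 0.088. The simulated increase was roughly 11% to 19%.

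**The case against.** **A reader might infer that the plan constrains covariate effects to be equal.** It does not say so. It lists covariates and is silent on covariate-by-time terms; common slopes are what the listed terms produce. The plan also promises: "We will carefully examine all model assumptions and reparameterize as indicated". That leaves room for such terms, but it names no term and no trigger, and adding one after seeing the data is weaker than prespecifying it. The point is therefore an omission.

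**A reader might infer that the main test of the trial, or of persistence, is at risk.** The interaction is explanatory. The primary test is a separate 6-week regression, and the planned area-under-the-curve analysis addresses the association across both visits without this term.

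**A reader might take the upper figures as expected.** They need both a marked fall in the slope and a negative direct link between sleep change and baseline dipping. Neither is documented. The built-in relation between change and baseline sleep efficiency gives only r(S,B) = −0.15.

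**A reader might extend the point to every Aim 2 mechanism.** The assessment sections put urinary catecholamines only before and after CBT-I, and pulse wave velocity only before CBT-I and at 6 months. Although C.5 opens by listing all four visits for its assessments, on these specific schedules neither outcome has both values for a joint model.

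**The exposure is not fully defined.** The plan does not say whether sleep efficiency in the interaction is the 6-week change or varies by visit. If it varies, the simple formula above does not apply. This objection stands, and the sizes are conditional on the fixed 6-week change.

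**Conclusion.** The concern holds as a modest gap in the specification of the follow-up model. As written, the model gives pre-treatment dipping one slope for both visits, and the explanatory time × sleep efficiency term is biased if that slope fades and sleep change correlates with baseline dipping. Under the stated assumptions the bias runs from about −0.03 to +0.095, so at most a little over a third of the 0.25 correlation that the study is powered to detect (0.095/0.25 = 0.38). Its sign depends on the sign of r(S,B). Rejection runs from about 5% to 23%. At correlations of 0.1 or less with a slope drop of 0.2, the effect is small. No primary conclusion and no sample size changes.

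**What to change.** Prespecify time × pre-treatment outcome in each joint 6-week/6-month model: the Aim 1 blood pressure outcomes, and the Aim 2 outcomes measured at both visits, such as flow-mediated dilation and lipids. Urinary catecholamines and pulse wave velocity need no such term on their stated schedules. The cost is one sentence in the plan, one degree of freedom per model and almost no precision.

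Time × baseline sleep efficiency, and in Aim 1 time × baseline 24-hour blood pressure, can be added as a sensitivity analysis. The sleep efficiency term costs roughly 11% to 19% in the standard error of the interaction, which is why it is better kept out of the main follow-up model. The same sentence should state whether sleep efficiency in the interaction is the 6-week change or a value for each visit.

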**ReScreening** - If a participant fails to meet all eligibility criteria, but remains interested in participating in the study, they will have the option to be rescreened at a future date. If the rescreening occurs within 3 months, only the eligibility criterion which made them ineligible initially will be reassessed in order to ascertain their eligibility at rescreening; if rescreening occurs after more than 3 months, then the full screening protocol will be repeated. The participant will be re-consented at the time of rescreening.

**Office BP Screening Assessment.** At the first lab screening session, BP will be determined by unattended automated office blood pressure (AOBP) measurement using the Omron HEM-907 Professional Intellisense BP Monitor. AOBP measurement minimizes the “white coat” effect and correlates more closely with ambulatory BP than do standard office measurement techniques. After seating the individual in a quiet room, a cuff of appropriate size will be wrapped around the individual’s non-dominant upper-arm and the Omron HEM-907 will be operated in automated mode: After starting the

monitor, the Research Assistant will leave the room, and after a lapsed time of 5 minutes, the monitor will take a total of three BP measurements, each 2 minutes apart; the average of these three readings will be used to define office BP at that visit. If BP meets the studies inclusion/exclusion criteria, a second screening session will be scheduled, and if BP continues to meet criteria, the individual will be enrolled as a study participant (assuming all other inclusion/exclusion criteria are also met). This method for office BP assessment also will be completed subsequently at all four laboratory assessment sessions.

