**Arterial Stiffness.** Aortic pulse wave velocity (PWV), measured using the Complior system (Artech Medical, Pantin, France), will be our validated index of central arterial stiffness. Pulse pressure waveforms will be recorded from the right carotid and right femoral arteries, and PWV through the descending aorta, measured in meter/sec, is calculated from measurements of pulse transit time and the distance travelled by the pulse, derived from the distance between the two recording sites. The PWV assessment will be performed by [name], RDMS, RVT, who has over 10 years of experience with this procedure. This will be performed pre-CBTI and at the 6 month follow-up.

**Blood Assays.** Blood will be drawn and processed by our research phlebotomist between 8:00 am and 10:00 am, after 12 hours of overnight fasting, on each of the four laboratory assessment visits, in order to measure: total cholesterol, HDL- and LDL-cholesterol, VLDL-cholesterol, and triglycerides; inflammatory activity measured by high sensitivity C-Reactive Protein (hsCRP); At baseline assessment only, thyroid stimulating hormone (TSH) will be assayed to ascertain if hypertension is due to hyper- or hypothyroidism.

**Atherosclerotic Cardiovascular Disease (ASCVD) Risk.** Although we are interested primarily in whether improved sleep quality will lower the mechanisms of insomnia-related CVD risk, we will also explore computed ASCVD risk (for participants aged  $\geq 40$  years) from the Pooled Cohort Equations recently validated and recommended by the clinical practice guideline expert panel of the American College of Cardiology/American Heart Association. These equations estimate the 10-year risk of a primary ASCVD event (including myocardial infarction and stroke) among patients without pre-existing CVD. Patients are considered to be at "elevated" risk if the Pooled Cohort Equations predicted risk is  $\geq 7.5\%$ . For example, a 50-year old white male smoker with a systolic BP of 130 mm Hg, no diabetes, and total cholesterol of 200 mg/dL with HDL cholesterol 30 mg/dL would have a 10-year ASCVD risk of 13.2%. Lowering systolic BP to 120 mm Hg and raising HDL to 50 mg/dL, with total cholesterol remaining at 200 mg/dL, would almost half his risk, reducing it to 6.9%. Indeed, we also have recently shown that both pharmacological and behavioral interventions to treat depression can lower the calculated 10-year risk of an ASCVD

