## Safety Monitoring

Although blood pressure will be monitored by research staff during the study, blood pressure management will continue to be up to participants' health care providers (HCPs). Patients who exhibit screening "office" averaged BP greater than 160/100 mm Hg across the two screening sessions will not be eligible to participate in the study and will be provided their screening BPs with the recommendation that they provide this information to their HCP within 72 hours. For participants already enrolled in the study, if "office" averaged BP values exceed 160/100 mm Hg, the participant will be provided those BP readings at that time, and will be encouraged to share the results with their HCP within 72 hours; with patient written consent, we also will provide the BP readings to their HCP. All eligible participants will have completed the CBT-I intervention within approximately 3 months from study enrollment. Both pre- and post-treatment ambulatory blood pressure records and study-assessed "office" blood pressures will be provided to participants at that time (i.e., after ~12 weeks), and with their consent (using a Redcap electronic medical authorization or paper authorization form), also will be provided to their HCP for follow-up as needed. In the event that participants do not have a HCP, a list of local family HCPs who are accepting new patients will be provided to them.

Participants will undergo follow-up assessments 6 months after the CBT-I intervention. Any intervening treatments including antihypertensive medications, will be documented. It should be emphasized that participants will not be prohibited from initiating pharmacologic treatment for high blood pressure at any time during the study. At all assessment phases, participants' medications will be documented. Upon completion of their participation in the study (approximately 9 months after initial screening assessments confirmed their eligibility), for participants who exhibit no improvement in their insomnia symptoms, we will refer them back to their HCP for consideration of alternative approaches to treating their insomnia.

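### The Aim 2 PWV model has no blood pressure term, so a sleep–PWV association that runs through lower visit pressure can be read as reduced arterial stiffness

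*Combined protocol and SAP*

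**What the plan says.** **Model.** In the ANALYSIS PLAN, Aim 2 outcomes are regressed on sleep-efficiency improvement, "controlling for age, gender, race, baseline sleep efficiency, and the pre-treatment (post run-in) level of the outcome". The one outcome-specific addition is "For our analyses of vascular endothelial function only, we also will adjust for baseline arterial diameter". The Aim 1 model does carry a pressure term ("baseline sleep efficiency, baseline mean 24-hour BP, and pretreatment BP dipping, with post-treatment BP dipping as the criterion"), but this is not brought into Aim 2.

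**Hypothesis and measure.** The third part of Hypothesis 2 is "iii) reduced arterial stiffness". Section C.5 (Arterial Stiffness) says that aortic PWV "will be our validated index of central arterial stiffness" and calculates it from pulse transit time and path length. No pressure correction is described. On timing, the same paragraph says: "This will be performed pre-CBTI and at the 6 month follow-up".

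**Pressure between the two readings.** Hypothesis 1 expects lower nighttime and 24-hour pressure with better sleep. Participants enter off antihypertensives, but Safety Monitoring says that "participants will not be prohibited from initiating pharmacologic treatment for high blood pressure at any time during the study". Medications are documented at each assessment phase. The analysis plan does not say how such starts are handled.

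**Pressure data available.** On automated office BP (AOBP), Design & Procedures says: "This method for office BP assessment also will be completed subsequently at all four laboratory assessment sessions".

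**The concern.** PWV rises and falls with the distending pressure at the time of recording, even if the arterial wall is unchanged. That is general physiology rather than a statement in the documents. If participants whose sleep improves most also have the larger falls in pressure at the PWV visit, the planned regression will show lower PWV with better sleep, whether or not stiffness has changed.

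Aim 2 is about mechanisms, and stiffness is listed apart from the pressure outcomes of Aim 1. A PWV result that only restates a pressure result would still satisfy Hypothesis 2(iii) as written. There is no control arm, so the interpretation rests on these regressions. What is at stake is the wording of one mechanistic conclusion; the primary outcome is not affected.

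**Working it through.** **1. Does anything else in the plan cover the path from pressure to PWV?**
- The pre-treatment PWV covariate carries part of baseline pressure, but not the change in pressure.
- The mediation analysis (Exploration of Mechanistic Relationships) runs from mechanism change to BP dipping, which is the opposite direction. It also uses mechanism changes from baseline to 6 weeks, and the PWV paragraph schedules no 6-week reading.
- No passage says how a PWV change that follows a pressure change will be interpreted.

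**2. The plan's own power figure.** The documents give none for PWV. The stated one concerns BP outcomes: 150 enrolled, 15% attrition, alpha 0.05, 80% power for r ≥ 0.25.
- n = 150 × 0.85 = 127.5, taken as 127.
- Power = Φ(atanh(r)·√(n − 3) − 1.96) = Φ(0.2554 × 11.136 − 1.96) = Φ(0.884) = 0.812.

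This reproduces the stated 80%. The present point does not alter it.

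**3. Illustration of the pathway.** Let *a* be the correlation of sleep-efficiency change with visit-pressure change, and *b* that of visit-pressure change with PWV change, both as magnitudes. Sleep has no direct effect on PWV. The correlation induced between sleep and PWV is then a × b, and with z = atanh(ab)·√124 the chance of P < .05 in the model without pressure is Φ(z − 1.96) + Φ(−z − 1.96).

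Example: a = 0.25 and b = 0.5 give ab = 0.125 and z = 0.1257 × 11.136 = 1.399. Then Φ(−0.561) + Φ(−3.359) = 0.288; simulation gives 0.286.

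Share of 20,000 simulated trials per cell (n = 127) with a significant sleep–PWV association, pressure not in the model:

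| a | b = 0.2 | b = 0.3 | b = 0.5 | b = 0.7 |
|---|---|---|---|---|
| 0 | 0.051 | 0.051 | 0.052 | 0.050 |
| 0.10 | 0.056 | 0.063 | 0.081 | 0.124 |
| 0.25 | 0.086 | 0.136 | 0.286 | 0.505 |
| 0.30 | 0.099 | 0.170 | 0.393 | 0.659 |

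With pressure change added, every cell lies between 0.046 and 0.051.

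**4. Limits of the illustration.** All values of *a* and *b* are assumptions. The documents give no correlation between pressure and PWV and no PWV variance. The values 0.25 and 0.30 are borrowed from the power section, where they concern sleep efficiency and BP outcomes or dipping, not pressure at a laboratory visit. The other model covariates are left out. Pressure is treated as measured without error at the PWV recording, so the return to 5% is a best case: a noisier reading would remove less.

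**The case against.** The strongest reply is that the plan claims no more than it tests. Hypothesis 2 says that better sleep will be accompanied by lower stiffness, and section A.2 describes the mechanisms as linked and cascading, not as independent of pressure. On that reading the model without pressure is the right estimate of the total association. This stands, and it is why the planned model should stay.

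Adjustment has its own problem. Pressure after treatment may mediate a sleep effect on the artery, or may itself result from stiffness. An adjusted estimate can then remove a real effect, and a loss of significance may reflect only low power. This also stands. It rules out making a stiffness claim depend on the adjusted P value, but it does not argue against showing the adjusted estimate.

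Third, Hypothesis 1 names dipping, nighttime and 24-hour pressure, not pressure at a daytime visit. A purely nocturnal fall would not lower distending pressure when PWV is recorded, and section A.2 calls a wider antihypertensive effect only possible. The pathway is therefore plausible, not established.

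A reader might infer that antihypertensive starts before the 6-month reading would be counted as a sleep benefit. The documents do not support a direction. Starts unrelated to sleep response mainly add noise. If poor sleep responders start treatment more often, a true association would be masked; only if good responders do so would it be inflated. Drug starts also affect the 6-month BP outcomes, so they are not peculiar to PWV. What remains is that the plan does not say how they will be handled.

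**Conclusion.** The omission is real and worth correcting. As written, the PWV analysis can show that sleep improvement goes with lower PWV, but it cannot say how much of that is lower pressure at the visit. The size is unknown from the documents: nil if visit pressure does not track sleep-efficiency change, and up to about 66% false attribution at the most extreme correlations assumed above. The conclusion rests on the pressure dependence of PWV and on some correlation between sleep change and visit pressure.

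Two stronger readings go too far. One is that a passive fall in PWV will be reported as reduced stiffness; that depends on conditions the documents do not establish. The other is a figure in m/s. Assuming 0.3–1.0 m/s per 10 mm Hg and a fall of 5–10 mm Hg gives 0.3 × 0.5 = 0.15 to 1.0 × 1.0 = 1.0 m/s, but neither input is in the documents. The result is also an average shift: a uniform fall in PWV creates no association with sleep-efficiency change, so it does not measure the bias in question.

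One of the four parts of Hypothesis 2 is affected. The primary outcome, sample size and stated power are not.

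**What to change.** 1. Keep the planned PWV model and label its result the total association of sleep improvement with PWV.
2. Pre-specify a companion model that adds mean arterial pressure at the pre-CBT-I and 6-month PWV visits, derived from the AOBP readings at those sessions.
3. Pre-specify a sensitivity analysis for documented antihypertensive starts before the 6-month PWV, for example with an indicator term and with those participants left out.
4. Report the planned and companion estimates side by side with confidence intervals. Describe a PWV change as pressure-independent stiffness only to the extent that the adjusted estimate and its interval support it. Do not use a P-value threshold as a veto.
5. Reconcile the PWV schedule. The PWV paragraph gives two readings, the introduction to section C.5 implies all four phases, and the Aim 2 follow-up model calls for both 6-week and 6-month values.

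**Cost.** No new visits and no change in sample size. The companion model uses two degrees of freedom: with 127 participants and one term each for gender and race, residual degrees of freedom go from 127 − 7 = 120 to 118. The adjusted estimate may over-adjust for a mediator, which is the reason for reporting both. AOBP is seated and is not stated to be simultaneous with PWV, so it is an imperfect proxy. A cuff reading at the PWV procedure itself would be better for any visits still to come, at the cost of a small addition to the procedure.
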